PCLX-001 was dosed as a bolus solution intravenously at 1 mg free base/kg (in saline) or by gavage orally as a solution at 10 mg free base/kg (in saline) to male beagle dog (n=3/dose route). Blood samples (10 μ L) were taken from each dog at 5, 15, 30 minutes, 1, 2, 4, 6, 8 and 24 hours post-dose, mixed with two volumes of distilled water and stored frozen until analysis.

Following intravenous administration at 1 mg free base/kg, PCLX-001 mean blood clearance was moderate at 22 mL/min/kg (~58% liver blood flow), mean volume of distribution (V_{ss}) was moderate at 4.3 L/kg, resulting in a moderate mean half-life at 2.3 hours. Mean AUC_{0-24} was 42,140 ng.min/mL.

Following oral administration at 10mg free base/kg, PCLX-001 had a mean C_{max} of 1229ng/mL and median t_{max} at 1.7 hours. Mean AUC_{0-24} is 560,220 ng.h/mL and mean bioavailability was 133%.

Pharmacokinetics Interpretation

The low volume of distribution observed in mouse (less than body water) appeared to be a mouse specific phenomenon. Improved efficacy may be seen in higher volume species through better distribution to the target such that there is no net change in potential therapeutic index.

In vitro ADME Profile

PCLX-001 (0.5 μ M) has low intrinsic clearance (Cl_{int}) in mouse, rat and human when incubated with liver microsomes, with Cl_{int} of <0.5, 1.0 and 0.7 mL/min/g respectively (using 52.5 mg microsomal protein/g liver). Cl_i in mouse and rat is consistent with the low *in vivo* Cl_B observed. Blood:plasma ratio was 0.59, 0.56, 0.69 and 0.50 in mouse, rat, dog and human respectively.

PCLX-001 has high (>99%) plasma protein binding in mice, rat, dog, and human plasma after 4 hour incubation at 5 μ M.

The cytochrome P450 enzymes (CYP) are a super family of hemethiolate enzymes responsible for the metabolic clearance of a wide variety of drugs. To characterize the metabolic clearance of PCLX-001, the relative contribution of CYP450 enzymes to the overall elimination process and the identification of the enzymes responsible for oxidative reactions were studied using native recombinant human CYP enzymes. These studies showed that PCLX-001 directly inhibited CYP3A4 (IC₅₀ of 12.1 μ M), CYP1A2 (40.6 μ M), CYP2B (63.02 μ M), CYP2C9 (52.3 μ M), and CYP2C19 (60.7 μ M). There was no inhibition of CYP2D6, CYP2E1, CYP2A6, or CYP2C8 (all with IC₅₀ > 100 μ M).

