PCLX-001 is a substrate for P-glycoprotein, as demonstrated by efflux studies in CaCo2 cells. It is not a substrate for or OAT1, OAT3, OCT1, OCT2, OATP1B1, OATP1B3, MATE1, MATE2K or BRCP. Overall, PCLX-001 shows a low probability for drug-drug interaction.

PCLX-001 was not mutagenic in the Ames test.

In vitro hERG Testing

A non-GLP study was done by a group developing a proprietary system for human ether-á-go-go-related (hERG) analysis (<https://www.achlys-inc.com/Cardiomyocytes>). The negative controls were acetylsalicylic acid and chloramphenicol and the positive control (determined IC₅₀ of 0.9 μ M) was Thioridazine Hydrochloride. PCLX-001 had a determined IC₅₀ of 9.9 μ M. This concentration was well above that expected to be achieved in a human phase I trial and suggests that PCLX-001 is likely not to be cardiotoxic.

KINOMEscan

PCLX-001 is a small molecule inhibitor that theoretically could also have the ability to inhibit kinases, and cause unexpected off-target effects. PCLX-001 was screened *in vitro* at concentrations of 0.5, 10, and 100 μ M (269, 5380, and 53,800 ng/mL) for its ability to inhibit the activity 468 human kinases. PCLX-001 at concentrations up to 10 μ M (5380 ng/mL) did not inhibit any kinase. PCLX-001 at 100 μ M (53,800 ng/mL), a concentration ~4000 x greater than the EC50 of PCLX-001 for BL2 cells, produced meaningful inhibition of only three kinases: MRCKA, PIP5K2B, and SRPK1. Based on these results, PCLX-001 is unlikely to produce adverse effects in patients due to off-target kinase inhibition and appears to be NMT-specific.

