- Any toxicity thought to be related to study drug which requires interruption of oral PCLX-001 for longer than 28 consecutive days from the time of scheduled dosing will be declared as a DLT.

In rare instances, an event may fall within the definition of a DLT as defined above but the event may not be considered dose-limiting (i.e. not clinically meaningful/significant). If this occurs, a meeting with investigators and sponsor will take place to thoroughly review the event, supporting data and reasons for not considering the event a DLT. This will be clearly documented with supporting rationale. Conversely, other events may occur which do not meet the definition of a DLT but are sufficient concern to the investigators and sponsor to be considered a DLT.

Maximum Tolerated Dose (MTD) is defined as the highest dose tested in which fewer than 33% of patients experienced DLT attributable to the study drug(s), when at least six patients were treated at that dose and are evaluable for toxicity. The MTD is one dose level below the lowest dose tested in which 33% or more patients experienced DLT attributable to the study drugs. At least six patients will be treated at the MTD.

Dose escalation and determination of the MTD will be based on the occurrence of DLT's in cycle 1. Patient safety will be monitored on an ongoing basis during this study. If cumulative toxicities are seen in subsequent treatment cycles, a decision regarding modification or discontinuation of the study drug and/or patient enrollment will be made by the investigator in consultation with the sponsor.

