4.2 Exclusion Criteria

The following exclusion criteria apply to ALL (Dose-escalation and expansion) patients:

1. Known hypersensitivity to the study drugs or excipients of the preparations or any agent given in association with this study
2. History of cardiac disease: congestive heart failure New York Heart Association (NYHA) class > II, unstable angina (angina symptoms at rest), new-onset angina (within the past 6 months before study entry), myocardial infarction within the past 6 months before study enrollment date, or uncontrolled cardiac arrhythmias
3. Uncontrolled arterial hypertension despite optimal medical management (per investigator's opinion)
4. Moderate or severe hepatic impairment, i.e. Child-Pugh class B or C
5. Patients with known human immunodeficiency virus (HIV) infection
6. Patients who have an active hepatitis B virus (HBV) or hepatitis C virus (HCV) infection requiring treatment. Patients with chronic HBV or HCV infection are eligible at the investigator's discretion provided that the disease is stable and sufficiently controlled under treatment.
7. Patients with significantly impaired liver function as assessed by the following laboratory tests to be conducted within 7 (± 3) days before the first dose of study drug:
 - Total bilirubin \geq 1.5 times the upper limit of normal (ULN), and/or
 - Alanine aminotransferase (ALT) and aspartate aminotransferase (AST) \geq 3 times ULN or \geq 5 times ULN for patients with malignant liver involvement.
8. Infections of CTCAE Grade 2 not responding to therapy or active clinically serious infections of CTCAE Grade > 2
9. Symptomatic metastatic brain or meningeal tumors unless the patient is $>$ 3 months from definitive therapy, has a stable imaging study within 4 weeks prior to the first dose of study drug and is clinically stable with respect to the tumor at the time of study entry. Patients with asymptomatic brain metastases must not be on steroid therapy. Patients with neurological symptoms should undergo a CT / MRI scan of the brain to exclude new or progressive brain metastases.
10. Current or past history of central nervous system (CNS) lymphoma

11. Uncontrolled seizure disorder requiring therapy (e.g. strong CYP3A4 inducers such as carbamazepine and phenytoin)

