23. Radiotherapy to target lesions in the 21 days before starting the first dose of study drug. Palliative radiotherapy is allowed to non-target lesions at any time before starting the first dose of study drug.
24. Major surgery or significant trauma within 4 weeks before the first dose of study drug
25. Previous assignment to treatment during this study
26. Concomitant participation in another clinical study with investigational medicinal product(s)
27. Substance abuse, medical, psychological, or social conditions that may interfere with the patient's participation in the study or evaluation of the study results
28. Close affiliation with the investigational site; e.g. a close relative of the investigator, dependent person (e.g. employee or student of the investigational site)
29. Use of strong CYP3A4 inhibitors and inducers from 14 days prior to first administration of study drug. Strong CYP3A4 inhibitors and inducers are prohibited during the study and until the active FU visit.
30. Use of Proton Pump Inhibitors (PPIs) must be discontinued at least 48 hours prior to initiation of study drug.

Note: If a potential participant is on a PPI and requires some form of Acid Reducing Agent(s) (ARAs), the investigator should consider alternatives for the duration of the trial, including Famotidine, or oral antacid drugs such as calcium carbonate.

31. Clinically relevant findings in the ECG such as a second- or third-degree atrioventricular block, prolongation of the QRS complex > 120 ms (except for bundle branch block pattern), or prolongation of the QTc interval (Fridericia) over 450 ms unless agreed otherwise between the investigator and the sponsor's medically responsible person.

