Note: If a potential participant is on a PPI and requires some form of acid reducing agent, the investigator should consider alternatives for the duration of the trial, including Famotidine, or oral antacid drugs such as calcium carbonate.
- Patients may not receive another investigational treatment or other approved antitumor therapy (such as chemotherapy) while on this protocol. In addition, treatment with "non-conventional therapies" (such as herbal supplements) is not permitted.
- The use of strong CYP3A4 inhibitors and inducers is not permitted from 5 days prior to first administration of study drug to the active FU visit.
- Patients should not receive PAXLOVID as components are known to inhibit CYP3A.
- Patients may not receive granulocyte colony-stimulating factor and other hematopoietic growth factors for primary prevention during Cycle 1.

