7.4 Pharmacokinetics

7.4.1 Drug Measurements

In patients enrolled in Part A dose escalation, serial blood (plasma) samples will be collected at the time points shown in Table 7C to assess PK of PCLX-001. For patients enrolled in Part B dose expansion, serial blood (plasma) samples will be collected at the pre-dose time points shown in Table 7D.

Whenever possible, all efforts should be made to adhere to the blood-sampling schedules given in Tables 7C and 7D. However, based on practical considerations, the following time ranges are provided as guidance:

Pre-dose samples should be collected within 15 min before the administration of PCLX-001. For 0.5 hours post dose, the PK sample should be collected within \pm 6 minutes. Subsequent PK samples should be collected \pm 15 minutes of planned time point. Sampling times outside these suggested intervals will not be considered as protocol deviations. The date and time of actual blood sampling and dose administration will have to be documented in the eCRF because PK calculations will be based on the actual sampling times relative to dosing times.

Cumulated substantial deviations of sampling times and / or consecutive, missing PK samples may lead to an insufficient (inadequate) description of the plasma concentration vs. time profiles of PCLX-001, and thus affect the quality of the PK evaluation of the respective patient(s). In this case, these deviations should be classified as “important” and may lead as declared “validity findings” to the exclusion of the respective patient(s) from the PK analysis set.

Details on sampling procedures, sample storage, and shipment are documented in separate sample handling documentation.

Table 7C: Schedule of pharmacokinetic blood sampling time points in Part A Dose Escalation

Procedures	Study Treatment Period 1 Cycle = 28 days								
	Cycle 1					Cycle 2		Cycle 3/ Beyond	EOT Visit
Visit Identifier (Visit Window)	Day 1	Day 2	Day 8 (±2)	Day 15 (±2)	Day 22 (±2)	Day 1 (± 2)	Day 15 (±2)	Day 1 (±2)	
	X	X	X	X	X	X	X	X	X
Pharmacokinetics									
Pre-dose* (-15 min)	X	X	X	X	X	X	X	X	X
0.5 hour (± 6 min)	X			X					
1 hours (± 15 min)	X			X					
2 hours (± 15 min)	X			X					
4 hours (± 15 min)	X			X					
8 hours (± 15 min)	X			X					

*If patient is receiving a dose on that day

Table 7D: Schedule of pharmacokinetic blood sampling time points in Part B Dose Expansion

Procedures	Study Treatment Period 1 Cycle = 28 days								
	Cycle 1					Cycle 2		Cycle 3/ Beyond	EOT Visit

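### Exclusion 29 sets a 14-day washout for strong CYP3A4 inhibitors and inducers and Section 6.1 sets 5 days; the passages must be reconciled

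*Combined protocol and SAP*

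**What the plan says.** Exclusion 29 in Section 4.2 rules out "Use of strong CYP3A4 inhibitors and inducers from 14 days prior to first administration of study drug" and adds that "Strong CYP3A4 inhibitors and inducers are prohibited during the study and until the active FU visit". The synopsis carries the same criterion with the same 14 days. Section 4.2 opens by stating its scope: "The following exclusion criteria apply to ALL (Dose-escalation and expansion) patients".

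The Prohibited Therapies list in Section 6.1 covers the same drug class and states that its use "is not permitted from 5 days prior to first administration of study drug to the active FU visit". It does not limit the 5 days to a subgroup or to one part of the study, and it does not refer to exclusion 29.

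Three other parts of the protocol bear on the consequence:

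- Section 3.2: "Dose escalation and determination of the MTD will be based on the occurrence of DLT's in cycle 1".
- Section 7.4.1: "In patients enrolled in Part A dose escalation, serial blood (plasma) samples will be collected at the time points shown in Table 7C". Table 7C places the full profiles on Cycle 1 Days 1 and 15.
- Section 8.2, Table 8-1: the PK population leaves out participants with significant violations of the inclusion or exclusion criteria.

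**The concern.** These are two start dates for one prohibition, both in current operative text. Section 6.1 is where site staff look when handling a patient's other medicines. A coordinator who takes the interval from there can judge a patient ready to start who is ineligible under Section 4.2.

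The stake is whether such a patient has violated an eligibility criterion. That determines whether a deviation is reportable under Section 10.4, and whether the patient's concentrations may be dropped from the PK population. PK is a primary objective. The patient would also start Cycle 1 sooner after a strong CYP3A4 drug than exclusion 29 intends, at the time when DLTs are counted and the PK profiles are drawn.

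**Working it through.** The plan gives no derived figure to reproduce. The check sets the passages side by side.

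**Inputs.** Exclusion 29 (synopsis and Section 4.2): prohibited from 14 days before the first dose. Section 6.1: prohibited from 5 days before. End of prohibition: the active follow-up visit in both.

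**Step 1: width of the gap.** 14 − 5 = 9 days. Counting the boundary day as prohibited in both rules, Section 4.2 covers days 1 to 14 before the first dose and Section 6.1 covers days 1 to 5. Days 6 to 14 are left, and 14 − 6 + 1 = 9.

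**Step 2: direction of the conflict.**

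| Last strong CYP3A4 drug, days before first dose | Section 6.1 | Exclusion 29 |
|---|---|---|
| 15 or more | complies | eligible |
| 6 to 14 | complies | excluded |
| 1 to 5 | breach | excluded |

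The 5-day window lies inside the 14-day window. Anyone who clears 14 days has cleared 5, so only the middle row is in conflict.

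**Step 3: is it a deliberate two-tier rule?** The proton pump inhibitor restriction is also stated in the synopsis, Section 4.2 and Section 6.1, and all three give 48 hours. Only the CYP3A4 interval differs, which looks like an oversight.

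**Step 4: could a site reach the gap in ordinary conduct?** Table 7A repeats the concomitant-medication check within 7 (± 3) days before the first dose, that is 7 − 3 = 4 to 7 + 3 = 10 days before. Suppose a strong CYP3A4 drug is found and last taken on the day of that visit, and the start date is kept. At 6 to 10 days the patient complies with Section 6.1 and fails exclusion 29. At 4 or 5 days the patient fails both.

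**Step 5: what a violation touches.** Table 8-1 makes a significant eligibility violation a ground for leaving the PK population. A patient in the middle row violates Section 4.2 while complying with Section 6.1, so the rule can be argued either way. The MTD-determining population has no eligibility condition, so the same patient would still count for DLT.

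**Step 6: timing against the PK profiles.** For a last dose 6 to 14 days before Day 1, the nominal Day 15 profile falls 6 + 14 = 20 to 14 + 14 = 28 days after it. Any residual effect would therefore bear more on the Day 1 profile than on the Day 15 profile.

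**The case against.** The strongest reply is that the eligibility criteria already settle the matter. Section 4 requires every criterion to be met and reviewed before enrolment. Section 7.2.1 admits a patient to treatment only once the investigator confirms this. Table 7B repeats the check on Cycle 1 Day 1 before dosing. Section 6.1 waives none of it, and because the windows are nested a site can obey both rules by applying the longer one. This stands. A reader might infer that the protocol permits treatment of a patient in the gap, or that a site must break one rule to follow the other. Neither is so: treating that patient would be an eligibility deviation. What remains is that no section states the order of precedence, and the section on concomitant medicines gives a different number.

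A reader might also infer that Cycle 1 exposure to PCLX-001 would be altered. The documents do not show this. Section 1.2.3 reports that "These studies showed that PCLX-001 directly inhibited CYP3A4", which concerns its effect on other drugs. No section names CYP3A4 as its clearance route, and the same section concludes: "Overall, PCLX-001 shows a low probability for drug-drug interaction". The prohibition itself, and the bar on PAXLOVID because its components inhibit CYP3A, show that the protocol treats CYP3A modulation as a precaution. They do not demonstrate an effect. Possible residual inhibition or induction is as far as the text goes.

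Finally, one patient is 1/6 to 1/3 of a dose level of 3 to 6, and one DLT turns 0/3 into 1/3. That is true of any patient in a 3+3 cohort and does not measure this problem.

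**Conclusion.** The contradiction is real: 14 days in two places, 5 days in a third, for the same drug class with the same end point. The disputed window is 9 days, from 6 to 14 days before the first dose, with the boundary day counted as prohibited in both rules. It works in one direction only, and exclusion 29 should catch the patient if sites apply it as written.

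The supported consequence is a risk of avoidable eligibility violations at a site working from Section 6.1, with an unclear place in the PK population for any patient affected. An effect on Cycle 1 exposure, and through it on DLTs, is possible. Its size cannot be calculated from the documents, which also give no basis for estimating how many patients would fall in the window. The point is a correction of an operative inconsistency and does not challenge the escalation design. No view is taken here on which interval is right.

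**What to change.** Reconcile exclusion 29 in the synopsis, exclusion 29 in Section 4.2 and the Prohibited Therapies entry in Section 6.1 to one washout interval, chosen by the sponsor and stated identically in all three places.

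For patients already enrolled, use the medication stop dates to identify anyone in the 6-to-14-day window, and bring those cases to the cohort safety review and the PK review. Section 6.1 already requires start and stop dates on the eCRF, and Table 7A collects prior and concomitant medications at screening, so no new data field is needed. One limit should be checked: the Section 6.1 record begins 7 days before the baseline evaluations, so it reaches back 14 days only if those evaluations began at least 14 − 7 = 7 days before the first dose. Otherwise the prior-medication entry must be relied on.

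The cost is a short text amendment and a one-off listing, with no extra patients, visits or procedures.

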7. STUDY SCHEDULE AND ASSESSMENTS

7.1 Study Calendar

The calendar below lists the assessments and indicates with an "X" the visits when they are performed. Baseline evaluations are to be conducted within 28 days (or 7 days as indicated) prior to start of protocol therapy. Diagnostic imaging and LVEF assessment must be done 28 days prior to the start of therapy. In the event that the patient's condition is deteriorating, laboratory evaluations should be repeated within 72 hours prior to initiation of the next cycle of therapy.

Table 7A: Schedule of Evaluations (Study Flow Chart) – SCREENING

Measures / actions	Screening	
	Within 28 days	Within 7 (± 3) days before the first dose of PCLX-001
Informed consent		
Signing of informed consent	X	
Archival tumor tissue ^a	X	
General screening procedures	X	
Check of inclusion / exclusion criteria	X	
Demographics	X	
Complete medical history including documentation of primary diagnosis ^b	X	
Abbreviated medical history		X
Baseline characteristics		
• Prior and concomitant medications (prescribed and OTC)	X	
• Baseline toxicities	X	
Assessment of toxicities (open questioning for AEs)		X
Concomitant medications (prescribed and OTC)		X
Physical examination ^j	X	
Vital signs		
• Blood pressure, heart rate, and body temperature	X	
Body weight and body height	X	
ECOG performance status assessment	X	
Cardiovascular safety assessment		
• 12-lead ECG (standard, triplicate)	X	
• MUGA scan or echocardiogram	X	

Table 7A: Schedule of Evaluations (Study Flow Chart) – SCREENING (continued)

Measures / actions	Screening	
	Within 28 days	Within 7 (± 3) days before the first dose of PCLX-001
Tumor assessment (CT or MRI) ⁱ	X	
Blood sample collection for tumor biomarker, if applicable (e.g. CA125, CEA)	X	
PET-CT (optional, NHL patients only) ^c	X	
Fresh tumor biopsy (optional) ^d		X
Blood sample collection for exploratory biomarker analyses		X
Blood / urine sample collection for laboratory safety assessments		
• Hematology ^e ,		X
• Blood chemistry ^f ,		X
• Calculation of eGFR by Cockcroft-Gault		X
• Coagulation (aPTT, PT/INR)		X
• Thyroid function (TSH and T ₄ [total or free per local standard])		X
• Virology (HBsAg, anti-HCV) ^g		X
• Pregnancy test (serum) ^h		X
• Urinalysis (dipstick)		X

- a. Archival tumor tissue is mandatory for patients enrolled in the dose escalation levels and expansion cohorts. This specimen could have been collected at any time from the initial diagnosis to study entry.
- b. Documentation of the primary diagnosis using the complete pathology report. Collection of baseline FLIPI, IPI, or MIPI scores for FL, DLBCL, and MCLC, respectively. Collection of staging information for patients with B-cell lymphoma.
- c. This scan should only be performed for NHL patients and is optional (i.e. not required for patients with other histologies). If a PET-CT is performed at screening, it should be repeated once after the sixth cycle if no progressive disease is detected during the course of treatment and / or to confirm complete response or disease progression.
- d. Collection of screening fresh tumor biopsy will be optional for patients enrolled in whom an archival biopsy is older than 6 months. The tumor biopsy will be obtained before the first dose of study drug (during the screening period when all other general screening procedures have been completed and patients are eligible for study treatment).
- e. Hematology includes CBC + differential (i.e. hemoglobin erythrocytes, leukocytes, platelets, MCV, RDW, hematocrit, neutrophils, lymphocytes, monocytes, eosinophils, basophils, immature granulocytes, nucleated RBCs).
- f. Blood chemistry includes: sodium, potassium, chloride, bicarbonate or total CO₂ (as per site practice), calcium, phosphate, magnesium, total protein, albumin, glucose, serum creatinine, urea, uric acid, total bilirubin, ALT, AST, LDH, alkaline phosphatase, lipase
- g. Virology includes: hepatitis B surface antigen (HBsAg), hepatitis B surface antibody (anti-HB-sAb), and hepatitis C virus antibody (anti-HCV)
- h. Only for women of reproductive potential (including women of reproductive potential whose partners are sterilized).
- i. CT of the relevant disease region for solid tumors and CT thorax, abdomen, pelvis \pm neck for NHL. Patients with neurological symptoms should undergo a CT or MRI brain to rule out brain metastases. The overseeing physician can use their judgement to choose the appropriate scan type to perform.
- j. A full physical exam is required at baseline/screening. The exam should review all body systems as follows: general appearance, respiratory, cardiovascular, abdomen, skin, head and neck, lymph nodes, thyroid, musculoskeletal, neurological, and if clinically indicated, any other systems (investigator to specify). Thyroid exams may be included as part of the head and neck review. If the review of head and neck is normal, the thyroid can also be considered normal.

Table 7B: Schedule of Evaluations (Study Flow Chart) – TREATMENT AND FOLLOW-UP

Measures / actions	Treatment ⁿ								FU	
	Cycle 1					Cycle 2		Cycle ≥ 3	EOT visit	Safety FU visit ^b
	D1 ^a	D2	D8	D15	D22	D1	D15	D1		Long-Term FU ^o
Before study drug administration										
Check of inclusion / exclusion criteria	X									
Abbreviated medical history	X		X	X	X	X	X	X	X	
Concomitant medications ^c	X		X	X	X	X		X	X	
Assessment of toxicities (AEs) ^d	X		X	X	X	X	X	X	X	
12-lead ECG (standard, triplicate)	X					X			X	X
Blood pressure, heart rate, & body temperature	X		X	X	X	X	X	X	X	
Physical examination ^l	X		X	X	X	X		X	X	X
Body weight	X		X	X	X	X	X	X	X	X
ECOG performance status assessment	X		X	X	X	X	X	X	X	X
Blood sample collection for biomarker analysis ^f	X					X		X	X	
Blood / urine sample collection for laboratory safety assessments										
• Hematology ^g	X		X	X	X	X	X	X	X	
• Blood chemistry ^h	X		X	X	X	X	X	X	X	
• Calculation of eGFR by Cockroft-Gault	X					X				
• Coagulation (aPTT; PT/INR)	X					X				
• Thyroid function (TSH and T ₄ [total or free per local standard])	X					X			X	
• Virology (HBV DNA, HCV RNA) ^m	X									
• Pregnancy test (serum or urine) ^j	X									
• Urinalysis (dipstick)	X			X		X			X	
Tumor assessment all tumors (CT or MRI) ⁱ							End of every second cycle			
PET-CT (optional, NHL patients only) ^k							Once after sixth cycle			
Blood sample collection for tumor marker, if applicable (e.g., CA125, CEA, PSA)							End of every second cycle			
Survival status										X ^o

Table 7B: Schedule of Evaluations (Study Flow Chart) – TREATMENT AND FOLLOW-UP (continued)

Measures / actions	Treatment								FU
	Cycle 1					Cycle 2		Cycle \geq 3	
	D1 ^a	D2	D8	D15	D22	D1	D15	D1	
Study drug administration									
Review of patient study medication diary and compliance of medication taken at home	X	X	X	X	X	X	X	X	
PCLX-001 administration at study center	X	X	X	X	X	X	X	X	
Before & after study drug administration									
PK sampling (plasma) for PCLX-001 ^e escalation	X	X	X	X	X	X	X	X	
PK sampling (plasma) for PCLX-001 ^e expansion	X			X		X		X	

- a. Any of the assessments scheduled before drug administration on C1D1 may be missed without protocol deviation if the same assessment has been obtained and reviewed within 3 days before the start of treatment (except PK and exploratory biomarker analysis).
- b. If a patient discontinues study treatment at any time during the study for any reason (except for patients who died, withdrew consent and objected to further data collection, or were lost to FU), an active FU assessment should be performed 30 days (± 4 days) after the last dose of the last study drug.
- c. Prescribed and OTC.
- d. Questioning for AEs will be conducted at clinic visits; in addition, spontaneous reports of AEs will be collected throughout the study.
- e. PK sampling: For patients in dose escalation, see Table 7C for schedule. For patients in dose expansion, see Table 7D for schedule.
- f. To be taken pre-dose of each cycle Day 1 within 60 min before the morning dose and EOT
- g. Hematology includes CBC + differential (i.e. hemoglobin erythrocytes, leukocytes, platelets, MCV, RDW, hematocrit, neutrophils, lymphocytes, monocytes, eosinophils, basophils, immature granulocytes, nucleated RBCs). Detection of CTCAE Grade 4 neutropenia (only Cycle 1) will trigger twice-weekly white blood cell counts to be performed, so that DLT determination can be made.
- h. Blood chemistry includes: sodium, potassium, chloride, bicarbonate or total CO² (as per site practice), calcium, phosphate, magnesium, total protein, albumin, glucose, serum creatinine, urea, uric acid, total bilirubin, ALT, AST, LDH, alkaline phosphatase, lipase.
- i. Window for tumour assessment is ± 5 days from Day 28 of the even-numbered cycles. CT of the relevant disease region for solid tumors and CT thorax, abdomen, pelvis \pm neck for NHL.
- j. Women of childbearing potential (including women of childbearing potential whose partners are sterilized) must have a negative pregnancy test.
- k. This scan should only be performed for NHL patients and is optional (i.e. not required for patients with other histologies). If a PET-CT is performed at screening, it should be repeated once after the sixth cycle if no progressive disease is detected during the course of treatment and / or to confirm complete response or disease progression.
- l. Exam to be symptom-directed.
- m. To be performed if clinically indicated (e.g. positive HBsAg and/or anti-HCV tests as performed during screening).
- n. Unless otherwise indicated, the window for visits is ± 2 days.
- o. Electronic records will be used to assess patient survival monthly (± 1 week) from the date of the follow-up visit.

